# **10.2 SECONDARY EFFICACY MEASURES**

Secondary efficacy endpoints include the following:

- Change in peak 6MWD from Baseline to Week 12
- Change in plasma concentration of NT-proBNP from Baseline to Week 16
- Change in trough 6MWD from Baseline to Week 15

As specified in Section 8.4 above, the hierarchical (fixed-sequence) testing procedure will be employed to control the overall alpha level at 0.05.

# 10.2.1 Change in Peak 6MWD at Week 12

The methodology for primary efficacy analysis of change in peak 6MWD at Week 16 will also be carried out for the Week 12 assessment, as described above in Section 10.1.1.2.

# 10.2.2 Change in NT-proBNP at Week 16

The efficacy endpoint of change in NT-proBNP assesses if inhaled treprostinil decreases the level of NT-proBNP at Week 16 over placebo in subjects with PH-ILD. The null and alternative hypotheses are:

$$H_0: \mu_1 = \mu_2$$
$$H_a: \mu_1 \neq \mu_2,$$

where  $\mu_1$  and  $\mu_2$  are the median change from Baseline to Week 16 in NT-proBNP of the inhaled treprostinil and placebo treatment groups, respectively.

The NT-proBNP values will be listed for all subjects, including the nominal time point, collection date/time, normal range and "High/Low" flag. The values and their respective changes from Baseline will be summarized for each assessment. The difference between treatment groups for the change from Baseline to Week 16 will be tested using the analysis of covariance with change from Baseline in NT-proBNP as the dependent variable, treatment as the fixed effect, and Baseline NT-proBNP as the covariate. The pseudo SAS code is as follows:

proc glm; class treatment; model BNP\_C=Treatment BNP\_B; run;

where BNP\_C is the change from Baseline to Week 16 in NT-proBNP and BNP\_B is the NT-proBNP at Baseline.

If assumptions (normality and equal variance) for the parametric test are violated, the nonparametric Wilcoxon rank-sum test will be used. For subjects who do not have NT-proBNP measurements at Week 16, the LOCF imputation will be used. The analyses will also be performed for the data without imputation for the missing measures.

As an exploratory analysis, the NT-proBNP at Week 8 will be analysed using the same method as the NT-proBNP at Week 16.

### 10.2.3 Change in Trough 6MWD at Week 15

The methodology for primary efficacy analysis of change in peak 6MWD described in Section 10.1.1.2 will also be carried out for the change in trough 6MWD from Baseline to Week 15. Missing trough 6MWD will be imputed as described in Table 8-2 in Section 8.3.1. The analysis will be repeated to include only subjects with trough 6MWD at Week 15 (ie, missing trough 6MWD at Week 15 is not imputed).

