# 8.1 COVARIATES

The primary efficacy analyses of change in 6MWD at Week 16 will be adjusted for Baseline 6MWD (as a continuous variable). For sensitivity analyses of the primary efficacy endpoints and the secondary/exploratory endpoints with continuous variables, the baseline measure will always be the covariate.

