### 8.4 MULTIPLE COMPARISONS AND MULTIPLICITY

The primary efficacy endpoint of change in 6MWD measured at peak exposure from Baseline to Week 16 will be tested at alpha level 0.05. If the primary efficacy endpoint is statistically significant at alpha level 0.05, the statistical tests for secondary efficacy endpoints will be performed.

To control the Type 1 error rate, the secondary efficacy endpoints will be tested using a hierarchical (fixed-sequence) testing procedure. The change from Baseline in peak 6MWD at Week 12 will be tested at a 2-sided Type 1 error rate of 0.05. The subsequent tests for change from Baseline in NT-proBNP at Week 16, and then the change from Baseline in trough 6MWD at Week 15, will be tested sequentially only if the preceding test is statistically significant.

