14.2.1.17	Summary of Effects of Baseline Hemodynamics and Baseline PFTs on Peak 6MWD by Week
14.2.2.1	Summary and Analysis of Peak 6MWD (meter) at Week 12 – Secondary Efficacy Endpoint
14.2.2.2	Summary and Analysis of Peak 6MWD (meter) at Weeks 4 and 8
14.2.3.1	Summary and Analysis of NT-proBNP (pg/mL) Data at Week 16 – Secondary Efficacy Endpoint
14.2.3.2	Summary and Analysis of NT-proBNP (pg/mL) Data at Week 16 – with Observed Case
14.2.3.3	Summary and Analysis of NT-proBNP (pg/mL) Data at Week 8
14.2.3.4	Summary and Analysis of NT-proBNP (pg/mL) Data at Week 8 with Observed Case
14.2.4.1	Summary and Analysis of Trough 6MWD (meter) at Week 15 – Secondary Efficacy Endpoint
14.2.4.2	Summary and Analysis of Trough 6MWD (meter) at Week 15 with Observed Case
14.2.5.1	Summary and Analysis of Clinical Worsening Events
14.2.5.2	Summary of Hospitalization Information
14.2.6.1	Summary and Analysis of SGRQ Total Score
14.2.6.2	Summary and Analysis of SGRQ Symptoms Score
14.2.6.3	Summary and Analysis of SGRQ Activity Score
14.2.6.4	Summary and Analysis of SGRQ Impacts Score
14.2.7	Summary and Analysis of Distance Saturation Product (DSP) (m%)
14.3.1.1	Overall Summary of Adverse Events and Exacerbations of Underlying Lung Diseases
14.3.1.2	Summary of Adverse Events by System Organ Class and Preferred Term
14.3.1.3	Summary of Adverse Events by Preferred Term
14.3.1.4	Summary of Deaths
14.3.1.5	Summary of Serious Adverse Events by System Organ Class and Preferred Term
14.3.1.6	Summary of Non-Serious Adverse Events by System Organ Class and Preferred Term
14.3.1.7	Summary of Adverse Events Probably or Possibly Related to Study Drug by System Organ Class and Preferred Term

Table Number	Table Title
14.3.1.8	Summary of Adverse Events Leading to Permanent Discontinuation of Study Drug by Preferred Term
14.3.1.9	Summary of Adverse Events by System Organ Class, Preferred Term, and Severity
14.3.1.10	Summary of Adverse Events by Study Drug Dose at AE Onset
14.3.2.1	List of Deaths
14.3.2.2	List of Serious Adverse Events
14.3.4.1	Summary of SpO2 (%) Measured by Pulse Oximetry
14.3.4.2	Categorical Summary of SpO2 (%) Measured by Pulse Oximetry
14.3.4.3	Summary of Heart Rate (beats/min) by Pulse Oximetry
14.3.4.4	Summary of Supplemental Oxygen Use
14.3.4.5	Summary of Supplemental Oxygen (L/min)
14.3.4.6	Summary of Pulmonary Function Test Results
14.3.4.7	Summary of Subjects with ≥20% Decrease in FEV1 from Baseline
14.3.4.8.1	Summary of Laboratory Data – Clinical Chemistry

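### The gatekeeping NT-proBNP test uses raw pg/mL change in both its first-line and fallback forms, and the fallback drops the baseline covariate; a log-scale ANCOVA would be a cheap improvement if effects are roughly proportional

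*SAP*

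**What the plan says.** SAP 10.2.2 specifies "analysis of covariance with change from Baseline in NT-proBNP as the dependent variable, treatment as the fixed effect, and Baseline NT-proBNP as the covariate". The accompanying code puts change and baseline into the model untransformed. SAP 8.5, the section on derived and transformed data, defines no transformation for NT-proBNP, and the table in SAP 15.1 is titled "Summary and Analysis of NT-proBNP (pg/mL) Data at Week 16".

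The same section provides a fallback: "If assumptions (normality and equal variance) for the parametric test are violated, the nonparametric Wilcoxon rank-sum test will be used". It names no diagnostic and no threshold. The Wilcoxon test takes no covariate, whereas SAP 8.1 states that for "the secondary/exploratory endpoints with continuous variables, the baseline measure will always be the covariate".

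The hypotheses are framed on medians: the two parameters "are the median change from Baseline to Week 16 in NT-proBNP of the inhaled treprostinil and placebo treatment groups, respectively".

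SAP 8.4 places NT-proBNP second among the three secondary endpoints, after peak 6MWD at Week 12 and before trough 6MWD at Week 15. NT-proBNP and trough 6MWD "will be tested sequentially only if the preceding test is statistically significant".

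**The concern.** NT-proBNP is a concentration bounded below by zero, and the eligibility criteria in Protocol 4.1 and 4.2 set no upper limit on it. If treatment acts in proportion to level, a 25% fall is 50 pg/mL for a subject at 200 pg/mL and 1,000 pg/mL for a subject at 4,000 pg/mL. In a raw-change ANCOVA the mean difference and its standard error are then driven largely by the highest subjects. The Wilcoxon fallback removes their leverage but still ranks raw changes, so subjects with the same proportional response get different ranks because they started at different levels. It also gives up the baseline adjustment.

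At stake is the power of a formally tested endpoint. If it misses a real effect, trough 6MWD cannot be tested at all. The primary endpoint, the Week 12 test and the sample size are not affected.

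**Working it through.** **The plan's own figure.** The only power statement (SAP 5, Protocol 10.2) is for peak 6MWD: 30 m difference, SD 75 m, two-sided 0.05, at least 90% power.
- n per arm = 2 × (1.960 + 1.282)² × 75² / 30² = 131.4, so 132; the plan uses 133, with power 0.904 (0.901 by the noncentral t).
- With 15% discontinuation, 133 / 0.85 = 156.5, so 157 per arm and 314 in total.

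This reproduces, but it says nothing about NT-proBNP. It supplies only the two arm sizes used below, 133 and 157.

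**Assumed inputs (not in the documents).** Log-normal values with median 500 pg/mL; between-subject log SD 1.0 or 1.3; SD of within-subject log change 0.6 or 0.8; placebo drift +15%; treatment ratio 0.80 or 0.75. That makes eight scenarios. The SAP names no assumption check, so a Shapiro-Wilk test on the raw ANCOVA residuals at 0.05 is assumed as the trigger.

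**Simulated power, 1,000 trials per scenario:**

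| | 133 per arm | 157 per arm |
|---|---|---|
| Raw-change ANCOVA on raw baseline | 22–67% | 22–75% |
| SAP two-step rule | 50–94% | 58–97% |
| Log-change ANCOVA on log baseline | 61–98% | 70–99% |
| Log gain over raw ANCOVA | 31–53 points | 23–55 points |
| Log gain over two-step rule | 4–13 points | 1–15 points |

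The two-step rule ended in Wilcoxon in every trial. A repeat of the eight scenarios gave raw ANCOVA 21–73%, two-step 52–97%, log ANCOVA 65–99%, and a gain over two-step of about 2–16 points. The differences between runs are of the size of simulation error: at 50% power, √(0.25/1,000) = 1.6 points.

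**Closed-form check of the log row.** Power ≈ Φ(|ln ratio| / (SD × √(2/n)) − 1.96).
- Ratio 0.80, SD 0.8, n = 157: 0.2231 / (0.8 × 0.1129) = 2.47; Φ(0.51) = 0.70.
- Ratio 0.75, SD 0.6, n = 157: 0.2877 / (0.6 × 0.1129) = 4.25; Φ(2.29) = 0.99.

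These match the ends of the simulated range.

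**Where the loss comes from.** Under assumed log-normal values, the top 5% of subjects carry 65–92% of the sum of squares of raw change, which explains the weak raw ANCOVA. For the fallback, most of the loss is due to scale. Wilcoxon on log change gains about 4–10 points over Wilcoxon on raw change at 133 per arm, while a baseline-adjusted rank test on raw change does no better than Wilcoxon (both 56–96% at 157 per arm). The dropped covariate is an inconsistency with SAP 8.1, but not the main source of lost power here.

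**Wider assumptions (133 per arm).** With baseline log SD 0.8–1.5, and either an SD of log change of 0.5–1.0 or a log-scale correlation of 0.70–0.85, and ratio 0.8 or 0.7, the gain over Wilcoxon is about 0–26 points. Type I error was 0.03–0.06 for all methods.

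**Where the gain reverses.**
- Heavy-tailed log changes (t, 3 df), 157 per arm, ratio 0.80: Wilcoxon 89–99%, log ANCOVA 72–92%, a loss of about 7–17 points. At 133 per arm, ratio 0.75, SD of log change 0.8: 0.94 against 0.85.
- Effect only in the top quarter of baseline values, ratio 0.70, 157 per arm: raw ANCOVA 25–45%, Wilcoxon 23–36%, log ANCOVA 17–27%. At 133 per arm with baseline log SD 1.2 and SD of log change 0.5: 0.52, 0.39 and 0.29.

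**The case against.** A reader might infer that a few high-value subjects will dominate the NT-proBNP result. The documents do not support that for the procedure as a whole. Skew strong enough to let them dominate the ANCOVA would normally trigger the Wilcoxon test, in which an extreme value counts only as a rank. It follows that the 23–55 point gap is measured against a model that would probably not be the one used; the fair comparator is the two-step rule. This part of the objection stands.

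It is also fair to say that the main scenarios favour the log model, because they assume log-normal data and a uniform proportional effect. The documents give no mean, SD, skewness or expected effect for NT-proBNP, and the reversals above are real. This stands as a limit on confidence. However, neither document posits heavy tails on the log scale or benefit confined to high baselines.

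Finally, the protocol endpoint is change in plasma concentration and the SAP hypotheses concern median change. A reader might take the log scale to be free of cost. It is not: it changes the estimand and requires the hypotheses to be restated. Medians are already among the planned summaries (SAP 8), so an absolute description remains available either way.

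**Conclusion.** The point holds as a cheap improvement, not as an error that invalidates the analysis. Both planned tests of a gatekeeping endpoint work on raw pg/mL change, and the fallback departs from SAP 8.1 by dropping baseline. If NT-proBNP is right-skewed and the effect roughly proportional, a log ANCOVA gains about 2–16 power points over the planned two-step procedure at 133–157 per arm. This rests on the assumed log-normal distribution, the assumed SDs and ratios, and an assumed normality check. Confidence is medium. A claim that the gain is certain or always large would go beyond the documents.

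**What to change.** Amend SAP 10.2.2 before unblinding:
- Make log(Week 16 NT-proBNP) minus log(Baseline NT-proBNP) the dependent variable, with treatment and log(Baseline NT-proBNP) as model terms.
- Restate the null hypothesis as a ratio of geometric means equal to 1.
- Report the back-transformed ratio with its 95% CI.
- Use the same log scale, adjusted for baseline, for the Week 8 analysis and for any rank-based fallback. The rank-residual method of SAP 10.1.1.2 could be applied to log change and log baseline. If a fallback is kept, state the check that triggers it.
- Keep raw pg/mL values and changes, including medians, as descriptive summaries.

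The cost is SAP wording and a small code change; no extra data or subjects are needed. The downside is that the formal result becomes a ratio instead of an absolute (median) change in concentration, and the power gain depends on an approximately proportional effect.

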5.2 RANDOMIZATION

Subjects will be randomized (1:1) to receive treatment with inhaled treprostinil (6 mcg/breath) or placebo. An IXRS will be utilized for the central randomization procedure. Sites will enter values of the qualifying 6MWT and the date the test was conducted into the IXRS and will be notified if the subject qualifies for the study.

All subjects will be randomized using a centrally administered stratified permuted block randomization, stratified by Baseline 6MWD (\leq 350 meters and > 350 meters).

Prior to randomization, site personnel should complete a Pre-Baseline Review Form for review and approval by the Medical Monitor.

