# 10.1.1.2 Primary Efficacy Analysis

All 6MWT data will be listed for all subjects. For each scheduled assessment, this listing will include the date test was performed (or date test was intended to be performed if subject is unable to attempt the test), start time of the test, nominal time point, last treatment dose, hours from last treatment dose to 6MWT start, if walk was attempted, total distance walked (in meters), whether subject received oxygen during the test, amount of supplemental oxygen, and any circumstances that adversely affected the walk (if any) including reason for not

attempting test (if any). The trough 6MWT measure will also be indicated. In addition, a listing of 6MWD with imputed values will be included for both peak and trough 6MWD data.

For the primary efficacy analysis, the effect of inhaled treprostinil versus placebo on change in peak 6MWD at Week 16 will be evaluated via analysis of covariance (ANCOVA). Change from Baseline in peak 6MWD is the dependent variable, and treatment and Baseline 6MWD are covariates in this ANCOVA model. Least squares means and standard errors for each treatment group, the least squares mean difference and its standard error, as well as a 95% confidence interval for the treatment group difference and p-value for treatment group comparison will be calculated from the ANCOVA model. This methodology will be carried out as follows:

- 1. Walk distances obtained after study drug termination or unblinding will be excluded (as described in Section 8).
- 2. Imputation rules in Table 8-1 will be applied.
- 3. The LOCF algorithm will be applied.
- ANCOVA will be conducted based on the pseudo SAS code: proc glm; class Treatment; model DistC = Treatment Dist0; run;

where DistC is the change from Baseline in peak 6MWD at Week 16 and Dist0 is the baseline measure of the 6MWD.

If the ANCOVA assumptions are violated, the primary efficacy analysis will be based on non-parametric analysis of covariance within the framework of the extended Cochran-Mantel-Haenszel test (Koch 1990, Koch 1998, Stokes 2000). Specifically, a Cochran-Mantel-Haenszel mean score test will be used on the standardized mid-ranks (ie, overall rank divided by the number of ranks +1, or "modified ridit" scores) of the residuals from an ordinary least squares regression with change from Baseline in peak 6MWD at Week 16 as a linear function of distance walked at Baseline (as a continuous variable). This methodology will be carried out as follows:

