### **10.3 EXPLORATORY EFFICACY MEASURES**

Exploratory efficacy endpoints include the following parameters:

- Change in peak 6MWD from Baseline to Week 4
- Change in peak 6MWD from Baseline to Week 8
- Change in quality of life as measured by SGRQ from Baseline to Week 16
- Time to clinical worsening will be evaluated as an exploratory endpoint from the time to randomization until 1 of the following criteria are met:
  - a. Hospitalization due to a cardiopulmonary indication
  - b. Decrease in 6MWD >15% from Baseline directly related to disease under study, at 2 consecutive visits and at least 24 hours apart
  - c. Death (all causes)
  - d. Lung transplantation
- Change in DSP from Baseline to Week 16

# 10.3.1 Change in Peak 6MWD at Weeks 4 and 8

The methodology for primary efficacy analysis of change in peak 6MWD described in Section 10.1.1.2 will also be carried out for the assessments obtained at Week 4 and Week 8.

# 10.3.2 Change in SGRQ at Week 16

The responses to the SGRQ questionnaire at Baseline and Week 16 will be converted to the Total score and 3 domain scores according to the SGRQ manual (Jones 2002). Scores for Total and each domain will range from 0 to 100, with higher scores indicating more limitations. Both individual item responses as well as calculated scores will be listed. The change from Baseline for the Total and 3 domain scores (Symptoms, Activity, and Impacts) will be calculated.

The Total score and for the 3 domain scores as well as their changes from Baseline will be summarized by treatment group using descriptive statistics.

For the Total score and each of the 3 domain scores, treatment differences (inhaled treprostinil vs. placebo) will be tested by using analysis of covariance with change from Baseline as the dependent variable, treatment as a fixed effect, and baseline score as the covariate. The analyses will be based on the observed data with no imputation.

The pseudo SAS code is as follows:

proc glm; class treatment; model Score\_C=Treatment Score\_B; run;

where Score\_C is the change from Baseline in Total score or each of the 3 domain scores and Score\_B is the corresponding score at Baseline.

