#### 10.3.3 Time to Clinical Worsening

• Data on the clinical worsening assessment page of the eCRF will be used to determine clinical worsening status. Investigator-reported clinical worsening events including the date (study day) of the event, category of the clinical worsening event, Baseline 6MWD, first 6MWT details, and second 6MWT details will be listed. The time to clinical worsening will be calculated according to the rules described in Table 8-3 in Section 8.5.

The number and percentage of subjects with any clinical worsening and with each category of clinical worsening will be summarized by treatment group. Time to clinical worsening will be summarized by treatment group using product-limit estimates calculated by the Kaplan-Meier method and displayed graphically as Kaplan-Meier curves. A tabular summary of this analysis will include the number of subjects at risk (sample size), estimated median duration, and a 95% confidence interval for the median duration for each treatment group. The log-rank test, adjusted for Baseline 6MWD category, will be used to calculate the p-value for treatment differences in the ITT population.

The SAS Procedure LIFETEST will be used. The pseudo SAS statements are listed below:

proc lifetest; time TimeToWorsening\*Censor\_Status(1); strata B\_6MWD / group = Treatment test=all; run;

where B\_6MWD denotes the categorical Baseline 6MWD variable ( $\leq$ 350 meters versus >350 meters).

In addition, the Cox proportional hazards model will be fit to obtain the hazard ratio and its associated 95% confidence interval. The model will include treatment and Baseline 6MWD as explanatory variables. The SAS procedure PHREG will be used. The pseudo SAS statements are listed below:

where Dist0 denotes the Baseline 6MWD variable (continuous). If it is determined that the proportional hazards assumption does not hold for Baseline 6MWD, a stratified analysis will be conducted. The above SAS code will be amended to remove Dist0 from the model statement and add the 'strata B\_6MWD;' statement.

If the proportional hazards assumption does not hold for the Cox model, the restricted mean survival time (RMST) and its associated standard error will be calculated for each treatment group at Week 16 (Royston 2013). A 95% confidence interval will be constructed for the difference in RMST between the 2 treatment groups at Week 16.

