# 10.3.4 Change in DSP

The DSP will be calculated, and DSP results will be included in the data listing for pulse oximetry. DSP values and their respective changes from Baseline to Week 16 will be summarized by treatment group. The difference between treatment groups for the change from Baseline to Week 16 will be tested using analysis of covariance with change from Baseline in DSP as the dependent variable, treatment as a fixed effect, and Baseline DSP measure as the covariate. The analyses will be based on the observed data with no imputation.

The pseudo SAS code is as follows:

proc glm; class treatment; model DSP\_C=Treatment DSP\_B; run;

where DSP\_C is the change from Baseline to Week 16 in DSP (m%) and DSP\_B is DSP at Baseline.

In addition, the DSP at Week 4, Week 8, and Week 12 will each be analyzed in the same way as the DSP at Week 16.

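### The NT-proBNP model and, less importantly, the SGRQ models omit the 6MWD randomisation stratum: valid, but possibly a little conservative

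*SAP*

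**What the plan says.** - **Design.** Protocol 5.2: "All subjects will be randomized using a centrally administered stratified permuted block randomization, stratified by Baseline 6MWD", in two levels, ≤350 m and >350 m. Protocol 3.1 and SAP 3 say the same. No other factor is named.
- **NT-proBNP, Week 16 (SAP 10.2.2).** The model has "treatment as the fixed effect, and Baseline NT-proBNP as the covariate". If normality or equal variance fails, "the nonparametric Wilcoxon rank-sum test will be used", with neither covariate nor stratum.
- **SGRQ (SAP 10.3.2).** The total and each domain score are modelled with "treatment as a fixed effect, and baseline score as the covariate".
- **General rule (SAP 8.1).** For "secondary/exploratory endpoints with continuous variables, the baseline measure will always be the covariate". Both models follow this rule.
- **Where walk distance does enter.** In the primary analysis (SAP 10.1.1.2), "treatment and Baseline 6MWD are covariates in this ANCOVA model", with distance continuous. The Week 4, 8, 12 and trough analyses reuse that method. In SAP 10.3.3, "The log-rank test, adjusted for Baseline 6MWD category, will be used", and the Cox model includes continuous Baseline 6MWD.
- **Testing order (SAP 8.4).** Week 16 peak 6MWD, Week 12 peak 6MWD, NT-proBNP, then trough 6MWD. Each is tested only if the one before it is significant.

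**The concern.** Stratified blocks hold the arms close to balance on the stratum, so chance differences in walk category add almost nothing to the true sampling variance of the treatment difference. A model without the stratum still counts the between-stratum variation as residual noise. If the stratum predicts the outcome beyond the endpoint's own baseline, the reported standard error then exceeds the true one and the p-value is too large.

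The plan is also uneven. It carries the design factor into an exploratory time-to-event test, but not into NT-proBNP, a secondary endpoint under formal type I error control. A narrow miss on NT-proBNP would also close the test of trough 6MWD. SGRQ is exploratory and outside the sequence, so nothing is gated on it.

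**Working it through.** **1. The plan's own figures.** SAP 5 gives a 30 m difference, SD 75 m, two-sided 0.05 and 90% power.
- n per arm = 2 × (1.960 + 1.282)² × 75² / 30² = 131.3, so 132. The plan uses 133, with power Φ(30 / (75 × √(2/133)) − 1.960) = 90.4%.
- 266 / 0.85 = 312.9, against a stated total of about 314.

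These reproduce, but they concern 6MWD only. No power is stated for NT-proBNP or SGRQ.

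**2. Inputs the documents do not give.** Let R² be the share of the planned model's residual variance explained by the stratum. The range 0 to 10% is assumed, as is the 80% starting power.

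**3. Closed form for a perfectly balanced stratum.** The true SE is √(1 − R²) times the SE that the planned model reports. Hence:
- reported SE / true SE = 1/√(1 − R²)
- type I error of the planned test = 2 × [1 − Φ(1.960/√(1 − R²))]
- power with the stratum added, when the planned test has 80% = Φ(0.8416 + 1.960 × (1/√(1 − R²) − 1))

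| R² | SE too wide by | Type I error, planned | Power, planned | Power, stratum added |
|---|---|---|---|---|
| 0% | 0.0% | 0.050 | 80.0% | 80.0% |
| 2% | 1.0% | 0.048 | 80.0% | 80.6% |
| 5% | 2.6% | 0.044 | 80.0% | 81.4% |
| 10% | 5.4% | 0.039 | 80.0% | 82.8% |

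At 10%, for example: 1/√0.90 = 1.0541; 0.8416 + 1.960 × 0.0541 = 0.9476; Φ(0.9476) = 82.8%.

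**4. Simulation.** The settings were 266 subjects, stratified permuted blocks of 4 (assumed block size), 10,000 null trials per setting and 4,000 with an effect. Here r is the partial correlation of *continuous* 6MWD with the outcome given the outcome's own baseline, assumed from 0 to 0.5. The category carries only part of it.

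Null case, with 20% / 50% of subjects above 350 m:

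| r | Type I error, planned model |
|---|---|
| 0 | 0.050 / 0.049 |
| 0.1 | 0.046 / 0.051 |
| 0.2 | 0.050 / 0.049 |
| 0.3 | 0.050 / 0.043 |
| 0.4 | 0.042 / 0.038 |
| 0.5 | 0.039 / 0.032 |

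With the category added, type I error lies between 0.046 and 0.054 throughout. For the planned model, reported and empirical SEs agree within 2% at r ≤ 0.2. At r = 0.5 with half the subjects above 350 m they are 0.123 and 0.113, so the reported one is about 9% too wide.

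Power, with 25% above 350 m and an effect sized for about 90% under the planned model:

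| r | Planned | + category | + continuous 6MWD |
|---|---|---|---|
| 0.2 | 90.0% | 90.6% | 91.0% |
| 0.3 | 88.9% | 89.8% | 91.2% |
| 0.5 | 91.0% | 93.2% | 96.1% |

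**5. The fallbacks compared.** If its assumptions fail, the 6MWD analysis moves to a rank method that still regresses out the baseline (SAP 10.1.1.2). NT-proBNP moves to a test that discards Baseline NT-proBNP as well as the stratum. That is probably the larger loss of precision; the documents give nothing from which to size it.

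**The case against.** **It is a stated rule.** SAP 8.1 prescribes exactly these models, so this is a choice about precision and not an undisclosed gap. That stands. But 8.1 gives no reason for leaving out the design factor, and pre-specifying a model does not make it more efficient.

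**The size is assumed and may be nil.** This stands. No passage links Baseline 6MWD to change in NT-proBNP or SGRQ beyond their own baselines. In the simulation the gain is at most about one power point at r = 0.2.

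**SGRQ carries little weight.** This stands. It is exploratory and analysed on observed cases, and it is included only for consistency.

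Three stronger readings are tempting, and the documents do not support them:
- *A reader might infer that the NT-proBNP and SGRQ inferences are invalid because the model ignores the design.* Under 1:1 stratified allocation the estimate is unbiased, and the error can only run toward caution. Apart from simulation error, no setting put the planned test above 5%.
- *A reader might put the gain at 80.8%, 82.0% or 84.0% for R² of 2%, 5% or 10%*, from Φ((1.960 + 0.8416)/√(1 − R²) − 1.960). That formula gives the planned statistic unit variance, whereas balance on the stratum has already reduced it. It overstates the gain.
- *A reader might treat continuous Baseline 6MWD as the stratification factor.* Only the two-level category is. Omitting variation within a stratum forgoes precision but does not make the reported SE too wide.

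**Conclusion.** The omission is certain and its consequence is small. The NT-proBNP ANCOVA and the SGRQ ANCOVAs leave out the only randomisation factor. They are valid, and may be conservative by an amount the documents do not let us fix. With a balanced stratum explaining 0 to 10% of residual variance, an 80% test gains between 0 and 2.8 power points. The point matters most for NT-proBNP, third in the overall order (second among the secondaries), because a miss there blocks trough 6MWD. The DSP model in SAP 10.3.4 has the same form, with "treatment as a fixed effect, and Baseline DSP measure as the covariate", but Baseline DSP already contains walk distance, so it is not pressed here. Severity: low.

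**What to change.** 1. Add the ≤350/>350 m category, as recorded at randomisation, to the GLM statements in SAP 10.2.2 and 10.3.2. Continuous Baseline 6MWD is an alternative and may gain more, but it adjusts for a related, different term; name one in advance.
2. Amend SAP 8.1 so that the covariates for NT-proBNP and SGRQ are the endpoint's own baseline plus the randomisation category.
3. If the NT-proBNP assumptions fail, replace the plain Wilcoxon test with the rank-based analysis of covariance already set out in SAP 10.1.1.2. Use Baseline NT-proBNP as the covariate, stratify the Cochran-Mantel-Haenszel test by the randomisation category, and state whether ranks and residuals are formed within strata.

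The cost is one term and one degree of freedom per model, plus a short change to the rank code. No new data or subjects are needed, and type I error stays at its nominal level. Protocol 10.3 requires the analysis plan to be final before the sponsor is unblinded, so the change has to be made before then; a covariate added later would look data-driven.
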